8.3 Adverse Event Reporting Requirements

The reporting period for this study is from initiation of study treatment through completion of Caphosol therapy; however after this time point, the investigator must report upon knowledge any study treatment related event meeting the expedited reporting criteria in the following table.

Regulatory Reports To	Criteria for Reporting	Timeframe	Form to Use	Copy AE To:
CHW IRB	UPIRSO: Any event which is unanticipated, involved new or increased risk to subjects, and was at least possibly related to study procedures through Day 60 or the start of a new treatment whichever is earlier	5 calendar days	SAE	MCW SAE Coordinator
	Other problems or events meeting the definition of UPIRSO			
MCW DSMC	Any event that counts toward a study stopping rule.	Within 24 hours of PI notification	SAE	MCW SAE Coordinator
	All unexpected grade 3, and all grade 4, and 5 adverse events, as well as any others requiring expedited reporting as defined in this protocol.	Grades 4 & 5 events must be reported to the DSMC within 5 calendar days of study staff's knowledge	SAE	MCW SAE Coordinator

If the SAE meets CHW IRB criteria for expedited reporting, then an official signed report is submitted to the IRB within 5 days. Adverse events which did not meet the CHW Prompt Reporting Criteria as outlined in the CHW IRB policy and procedure should be reported to the IRB at time of continuing review. All deaths, regardless of the cause, need to be reported to the PI within 48 hours and then reported to the IRB.

The Study Coordinator will provide the MCW's Data and Safety Monitoring Committee (DSMC) and CHW IRB with the SAE in an appropriate format depending on the individual SAE (as reported or in a summary format).

9.0 STUDY DATA COLLECTION AND MONITORING

9.1 Data Management

Data management will be performed utilizing an electronic clinical trials management system called OnCore. OnCore is a secure, web-based application designed exclusively to support research protocols

Once an institution consents a patient, they will enter the patient demographics into the OnCore system and assign a study ID. Any paper data (i.e. safety reports, reports generated

from OnCore) will be kept in a locked and secure location within the MACC Fund Center Clinical Trials Office of the Pediatric Hematology/Oncology and Bone Marrow Transplant Program. The Clinical Trials Office has secure, electronic employee badge access only. Any paper data that is generated will be kept for at least 10 years.

9.2 Case Report Forms

Participant data will be collected using protocol specific electronic case report forms (e-CRFs) developed within OnCore based on its library of standardized forms. The e-CRF will be approved by the study Principal Investigator and the Biostatistician prior to release for use. The Study Coordinator or designee will be responsible for registering the patient into OnCore at time of study entry, completing e-CRFs based on the patient specific calendar, and updating the patient record until the end of required study participation.

9.3 Data and Safety Monitoring Plan (DSMP)

The study's Data and Safety Monitoring Plan will be in compliance with the Medical College of Wisconsin Cancer Center's Data & Safety Monitoring Plan (DSMP).

This study will be reviewed by the Medical College of Wisconsin Cancer Center Data and Safety Monitoring Committee (MCWCC DSMC). A summary of the MCWCC DSMC activities are as follows:

- Review the clinical trial for data integrity and safety.
- Review all unexpected grade 3, and all grade 4, and 5 adverse events, as well as any others requiring expedited reporting as defined in this protocol. (Grades 4 & 5 events must be reported to the DSMC within 5 calendar days of study staff's knowledge.)
- Review all DSM reports.
- Submit a summary of any recommendations related to study conduct.
- Terminate the study if deemed unsafe for patients.

A copy of the MCWCC Data and Safety Monitoring Plan and membership roster will be maintained in the study research file and updated as membership changes. The committee will review reports from the study PI twice annually (or more frequently if needed) and provide recommendations on trial continuation, suspension or termination as necessary.

Any available DSMC letters will be submitted to the IRB of record as required.

For the purposes of data and safety monitoring, this study is classified as moderate risk. Therefore the following requirements will be fulfilled:

- The PI will complete and submit a semi-annual Study Progress Report to the MCW Cancer Center Data and Safety Monitoring Committee (DSMC) with the understanding the MCW DSMC may require more frequent reporting.
- This protocol will be monitored by an individual or group of individuals from the MCW Cancer Center who are not directly or indirectly responsible for the supervision of this trial. Monitoring will occur at a minimum of once per year to ensure all regulatory aspects of this study are in compliance with the FDA and any other

applicable regulatory boards/bodies.

- The PI will oversee the submission of all reportable events per the definition of reportable in Section 8.3 to the MCW Cancer Center's DSMC and the CHW IRB.

9.4 Monitoring

The investigator will permit study-related monitoring, audits, and inspections by the MCW compliance groups. The investigator will make available all study related documents (e.g. source documents, regulatory documents, data collection instruments, study data, etc.). The investigator will ensure the capability for inspections of applicable study-related facilities (e.g. pharmacy, diagnostic laboratory, etc.) will be available for trial related monitoring, audits, or regulatory inspections.

9.5 Record Retention

The investigator will retain study records including source data, copies of case report forms, consent forms, HIPAA authorizations, and all study correspondence in a secured facility for at least 10 years after the study file is closed with the IRB.

In addition, the MACC Fund Center Clinical Trials Office (CTO) will keep a master log of all patients participating in the study with sufficient information to allow retrieval of the medical records for that patient. Please contact the CTO before destroying any study related records.

10.0 STATISTICAL CONSIDERATIONS

10.1 Statistic Endpoints

The study will not stratify based on diagnosis. The effectiveness of the study will be based on comparing incidence and severity of oral mucositis. Safety and tolerance will be based on the differential incidence of severe adverse events. A continuous sequential boundary will be used to terminate the study if the difference in adverse events occurs at a rate of 10% or greater at the interim analysis performed at the end of study month 3. A continuous sequential boundary will also be constructed for a differential rate of 5%.

An interim analysis will be conducted half way through using the O'Brien-Fleming rule for early stopping because of success.

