2.1 Study Design

This is a randomized controlled trial designed for the purpose of evaluating the efficacy and tolerability of Caphosol therapy for the prevention of oral mucositis (Grade ≥ 2) in children, adolescents and young adults at risk for developing oral mucositis due to their cancer therapy.

Our hypothesis is that by initiating Caphosol at the initiation of chemotherapy administration, we will decrease the incidence and/or severity of oral mucositis (Grade 3 or 4) as well as limit the number of days requiring narcotic analgesics, days of hospitalization and need/duration of total parental nutrition in patients randomized to the treatment group compared to the control group.

Primary Objectives

- To determine if topically administered Caphosol at the initiation of chemotherapy prevents the development of oral mucositis (Grade ≥ 2) in children, adolescents and young adults.
- To determine the tolerability of four times daily Caphosol therapy.

Secondary Objectives

To determine if topically administered Caphosol reduces the severity of oral mucositis, as measured by incidence of severe mucositis (CTCAE v4.0 Grades 3 or 4), age-appropriate pain scores, use of narcotic pain medicine, number of hospital days and number of days on TPN.

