- Incidence of oral mucositis. Oral mucositis will be defined and characterized by the Common Terminology Criteria for Adverse Events (CTCAE) Version 4.0 as Grade 1-4.
- Severity of oral mucositis, according to:
 - Age-appropriate pain scales (LIKERT and FACES)
 - CTCAE V 4.0 grading
 - Total narcotic usage (both the total amounts in milligrams and the number of days the patient required intravenous narcotic therapy as well as any increase of dose above baseline for patients who are on scheduled chronic use of narcotics)
 - Number of hospital days with oral mucositis present
 - TPN use and duration

The following will be observed on all patients on the Caphosol arm, via the study diary:

- Missed doses of Caphosol and reason
- Side effects attributed to Caphosol therapy
- Use of any other oral topical agents for oral mucositis (dose, schedule, number of doses taken) such as biotene/ chlorhexidine rinses and/or magic mouthwash.
- Use of any non-narcotic pain medications for oral mucositis (dose, schedule, number of doses taken)
- Use of any narcotics for oral mucositis (dose, schedule, number of doses taken)

The following will be observed on all patients on the Biotene arm, via the study diary:

- Use of any other oral topical agents for oral mucositis (dose, schedule, number of doses taken) such as chlorhexidine rinses and/or magic mouthwash.
- Use of any non-narcotic pain medications for oral mucositis (dose, schedule, number of doses taken)
- Use of any narcotics for oral mucositis (dose, schedule, number of doses taken)

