5.4 Duration of Therapy

Caphosol will be initiated on Day 1 of scheduled cancer therapy and will continue for:

- 7 days after therapy completion

AND

- ANC > 500 after nadir (count recovery)*

OR

- Resolution of oral mucositis symptom*

*(whichever occurs last)

Caphosol will be continued each time the patient receives chemotherapy where eligibility criteria are met for patients randomized to Caphosol arm.

Caphosol will be discontinued for allergy or patient intolerance. Please see Section 5.6 for criteria for removal from protocol therapy and off study criteria.

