5.6 Criteria for Removal from Protocol Therapy and Off-Study Criteria

5.6.1 Criteria for Removal from Protocol Therapy

- Completion of planned Caphosol therapy (all eligible chemotherapy cycles have been completed)
- Physician determines it is in the patient's best interest
- Adverse Event/Side Effects/Complications which based on the treating physician or patient/family opinion warrant coming off protocol therapy
- Inevaluable
- Patient Intolerance/Refusal

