7.1.7 Side Effects

No side effects are expected. Previous studies have shown Caphosol to be safe and well-tolerated with no known side effects, even when inadvertently swallowed.

Pregnancy: It is not known if Caphosol is teratogenic or passes through breast milk; therefore, pregnant and lactating patients will not be eligible for enrollment on study. Patients who become pregnant while on study receiving Caphosol will become ineligible and removed from protocol therapy.

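### Tolerability is a primary objective, but 10.1 measures it by a severe-adverse-event difference and 10.3 by an undefined Caphosol-arm toxicity, and neither uses the missed-dose, side-effect or intolerance data collected

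*Combined protocol and SAP*

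**What the plan says.** The Synopsis and Section 2.1 list as a primary objective: "To determine the tolerability of four times daily Caphosol therapy".

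Section 10.1 gives the basis for judging it: "Safety and tolerance will be based on the differential incidence of severe adverse events". The same section adds a sequential boundary to "terminate the study if the difference in adverse events occurs at a rate of 10% or greater", and a second boundary for a 5% differential. It does not say which grades count as severe.

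Section 10.3 describes something different. It says toxicity is estimable only in the treated group and gives a 95% CI of about 15 points either side from 48 Caphosol patients. A preliminary estimate is planned at 20 per arm. It also sizes a between-group comparison on a toxicity scale that is not defined.

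Data closer to the objective are collected elsewhere:

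- Section 5.0 has the Caphosol-arm diary record "Missed doses of Caphosol and reason" and "Side effects attributed to Caphosol therapy". The Biotene-arm diary list has no missed-dose item.
- Section 5.4: "Caphosol will be discontinued for allergy or patient intolerance".
- Section 5.6.1 lists "Patient Intolerance/Refusal" as a removal criterion, separate from its criterion for adverse events and side effects.

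On toxicity from the rinse itself, Section 7.1.7 says "No side effects are expected", and Section 8.2 says the same of toxicities.

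**The concern.** The objective asks whether children and young adults can keep up a four-times-daily rinse. A child who gags, refuses or gives up has not tolerated it, and need not have had any severe adverse event. The protocol recognises this outside Section 10: intolerance or refusal is its own reason for removal, and Sections 5.2 and 7.1.5 provide for young patients who cannot manage the full volume. In Section 10, tolerance becomes a difference in severe events in one place and an undefined toxicity in another.

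The severe-event difference suits this purpose poorly for two reasons. Every patient receives at least one listed chemotherapy agent (Section 3.1) and the rinse is expected to add no toxicity, so most severe events should come from cancer treatment in both arms. In addition, Grade 3-4 oral mucositis is a secondary efficacy outcome and is not excluded from the count, so a benefit on mucositis could offset an excess of other events.

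At stake is a primary objective that the planned analysis would leave largely unanswered. Section 10.3 calls the trial a pilot for a larger study, for which an estimate of adherence and intolerance would be especially useful.

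**Working it through.** **Inputs.** From the documents: 48 per arm at completion and 20 per arm at the toxicity look (10.3); 10-point and 5-point differentials (10.1); alpha 0.05, taken as two-sided because 10.3 does not say. Assumed: a background severe-event rate of 30-50%, with 2%, 10% and 70% as sensitivity values.

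**1. The plan's own precision figure.** For one proportion the half-width is 1.96·√[p(1−p)/n]. At p = 0.5 and n = 48, 1.96·√(0.25/48) = 14.1 points. The exact (Clopper-Pearson) interval for 24/48 is 35.2% to 64.8%, a half-width of 14.8 points. The stated figure of about 15 points therefore reproduces, as the worst case for a proportion in one arm.

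**2. Precision of the 10.1 measure.** For a difference with equal rates, the half-width is 1.96·√[2p(1−p)/n].

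| Assumed background | n = 48 per arm | n = 20 per arm |
|---|---|---|
| 30% | 1.96·√(0.42/48) = 18.3 points | 1.96·√(0.42/20) = 28.4 points |
| 50% | 1.96·√(0.50/48) = 20.0 points | 1.96·√(0.50/20) = 31.0 points |

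**3. Power for the plan's 10-point differential at 48 per arm.** With d = p1 − p2 and p̄ the mean of the two rates, power = Φ{(d − 1.96·√[2p̄(1−p̄)/n]) / √([p1(1−p1)+p2(1−p2)]/n)}. For 40% against 30%: (0.100 − 0.191)/0.0968 = −0.94, so power is 17%.

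| Assumed background | Power, 10-point excess | Fisher exact power | n per arm for 80% power (normal approximation) |
|---|---|---|---|
| 2% | 48% | 29% | 102 |
| 10% | 28% | 18% | 199 |
| 30% | 17% | 12% | 356 |
| 50% | 16% | 12% | 388 |
| 70% | 20% | 15% | 294 |

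Power for a 5-point excess is 7% to 22% over the same range. With no true difference, an observed Caphosol-arm excess of at least 10 points has probability 16-18% at 48 per arm and 30-32% at 20 per arm (backgrounds of 30-70%).

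**4. Precision of a Caphosol-arm proportion with 48 patients (exact 95% CI).**

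| Patients with the outcome | 95% CI |
|---|---|
| 0/48 | 0 to 7.4% |
| 4/48 | 2.3 to 20.0% |
| 12/48 | 13.6 to 39.6% |
| 24/48 | 35.2 to 64.8% |

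The half-width is at most 14.8 points at 48 patients and at most 22.8 points at 20. Over the 30-50% range used in step 2, the simple formula gives 13.0 to 14.1 points at 48.

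**5. Coverage of the objective in Section 10.** Section 10.1 covers severe events, between arms. Section 10.2 contains no analysis of missed doses, adherence, attributed side effects or stopping for intolerance. Section 10.3 covers toxicity in one arm plus a two-group toxicity scale, with neither defined nor linked to the diary. Sections 10.1 and 10.3 also disagree on whether the quantity is comparative.

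**The case against.** The strongest reply is that Section 10.3 already plans a Caphosol-only interval, with essentially the precision available from any single-arm proportion. That stands, and it means the severe-event difference is not the plan's only statement. It does not settle the matter, because toxicity is left undefined, is not tied to doses or discontinuation, and conflicts with 10.1.

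A reader might infer that the plan would declare the rinse tolerable whenever severe events were balanced, even if many patients refused it. The documents do not support this. They contain no rule for declaring tolerability, only a basis for assessment and a stopping boundary. Nor would refusals go unseen: diaries are reviewed at study visits (2.0), outpatients are checked for compliance (7.1.6), and refusal is a removal criterion. What is missing is a planned analysis of these data.

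A reader might also take it as established that chemotherapy dominates the severe events. It is a sound inference from Sections 3.1, 7.1.7 and 8.2, but no rate is given. Randomisation also prevents the chemotherapy background from biasing the comparison; what remains is noise.

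Finally, the interval widths for an arm difference and a single-arm proportion describe different quantities. The narrower one is not better for being narrower. The argument for the proportion is that it addresses the objective.

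**Conclusion.** The concern holds in this form: Section 10 ties a primary objective to a measure that mostly reflects something else, adds a second, conflicting and undefined measure, and plans no analysis of the data that bear on it directly. This should be corrected; nothing in it calls for a change in sample size.

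The numerical part depends on the assumed background. At 30-50%, the severe-event difference is known only to about 18-20 points at 48 per arm, roughly twice the 10-point differential the plan treats as important. At a background as low as 2% power improves but is still below 50%. The mismatch with the objective does not depend on the background rate: even a precise severe-event difference would not count missed doses or refusals.

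**What to change.** In Section 10.1, keep the severe-adverse-event comparison as the safety endpoint, state which grades count as severe, and say whether Grade 3-4 oral mucositis is included. Define tolerability separately, as Caphosol-arm estimates with exact 95% CIs:

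- (a) the proportion of patients who stop Caphosol for intolerance or refusal during any course;
- (b) the proportion who take at least a pre-specified share of the base four-daily doses over the protocol-defined treatment period.

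Tabulate missed doses by recorded reason, and list the side effects attributed to Caphosol.

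Fix the cut-off and the denominator in advance. Use of the rinse may rise to six times daily, and duration depends on neutrophil recovery and mucositis resolution, so the number of expected doses varies between patients. State how missing diaries, and reduced-volume or swab-applied doses, are counted. Do not limit (a) to one course, because Caphosol continues through each eligible course and later refusals would be lost.

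In Section 10.3, state that the interval of about 15 points applies to these single-arm proportions, define or remove the toxicity scale, and reconcile the statement that toxicity is estimable only in the treated group with the between-arm difference in 10.1.

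The cost is an SAP amendment and a short set of tables, with no new data items and no more patients. The limitation is that the result is descriptive and uncontrolled: missed doses are not recorded in the Biotene arm, diaries are self- or family-reported, and doses missed through chemotherapy illness or mouth pain can be separated from intolerance of the rinse only through the recorded reasons.

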2	02/24/2016	
Added updated DSMC language as requested by the MCW DSMC on 1/22/15:
 
This study will be reviewed by the Medical College of Wisconsin Cancer Center Data and Safety Monitoring Committee (MCWCC DSMC). A summary of the MCWCC DSMC activities are as follows:
 
 • Review the clinical trial for data integrity and safety. • Review all unexpected grade 3, and all grade 4, and 5 adverse events, as well as any others requiring expedited reporting as defined in this protocol. (Grades 4 & 5 events must be reported to the DSMC within 5 calendar days of study staff’s knowledge.) • Review all DSM reports. • Submit a summary of any recommendations related to study conduct. • Terminate the study if deemed unsafe for patients. 
A copy of the MCWCC Data and Safety Monitoring Plan and membership roster will be maintained in the study research file and updated as membership changes. The committee will review reports from the study PI twice annually (or more frequently if needed) and provide recommendations on trial continuation, suspension or termination as necessary. Any available DSMC letters will be submitted to the IRB of record as required.
	
YES –
 
Footers/Headers only– updated to protocol v2 Dated 2/24/2016
 
 • Consent Spanish Short Form • HIPAA Adult • HIPAA Adult Spanish • HIPAA Child • HIPAA Child Spanish

SYNOPSIS

Study Title: A Randomized Controlled Trial Investigating Topical Caphosol for Prevention of Oral Mucositis in Children, Adolescents and Young Adults (AYA) Receiving Chemotherapy

Randomized Controlled Trial

[figure not shown]
Number of Patients: A total of 96 patients will enroll to this study with 48 patients in the Caphosol group and 48 patients in the control group.

Study Objectives

- **Primary Objectives**
 - To determine if topically administered Caphosol at the initiation of chemotherapy prevents the development of oral mucositis (Grade ≥ 2) in children, adolescents and young adults.
 - To determine the tolerability of four times daily Caphosol therapy.

- **Secondary Objectives**
 - To determine if topically administered Caphosol reduces the severity of oral mucositis, as measured by incidence of severe mucositis (CTCAE v4.0 Grades 3 or 4), age-appropriate pain scores (FACES and Likert), use of narcotic pain medicine, number of hospital days and duration of total parenteral nutrition (TPN).

Treatment Plan Schema

Caphosol Administration:

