10.2 Statistical Analysis

Comparisons of binary outcomes such as prevention of oral mucositis will use logistic analysis or Fisher's exact test if the numbers are small. Comparisons of the severity of oral mucositis (an ordinal scale) will use the Wilcoxon rank sum test since the data is on a 5 point Likert scale, although there are really only two levels of values. Similarly for the secondary outcome an ordinal pain scale can be treated as an ordinal scale. Length of stay and duration of TPN will use a t-test plus a log transform, if necessary to reduce the skewness of the data. Otherwise the Wilcoxon test will be used.

Although there may be loss to follow-up, we don't expect it because continued

chemotherapy depends on the clearing of the mucositis.

The primary analysis for mucositis will be based on a binary scale (Grade 1 versus Grade ≥ 2 mucositis) because the mucositis essentially has only two clinically pieces to the scale. It also represents common clinical practice.

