10.3 Sample Size Justification

For an alpha of 0.05 and a power of 80%, 48 subjects per group allow detection of a 30% difference in the incidence of oral mucositis (range of oral mucositis is 25% to 50%). Efficacy assessment will occur at study completion.

Twenty subjects per group can detect a 0.6 unit difference in the toxicity scale. This is based on an effect size of 0.90 and a SD of 0.66 units. This is a medium sized clinical difference using Cohen's criteria. This study will serve as a pilot for a larger study. For toxicity, which can only be estimated in the treatment group, 48 subjects in the Caphosol group will allow estimation of a 95% confidence interval of the toxicity of about $\pm 15\%$. Assessment of toxicity will occur once the study enrolls 20 patients to each arm to obtain a preliminary estimate (95% CI) for toxicity and again at study completion (to obtain a more precise estimate). While the study is stopped if it passes the sequential boundary, to obtain an estimate of the toxicity and its 95% Confidence interval (95% CI) both an interim analysis and an analysis at the end of the study will be used to estimate the 95% CI – most precisely at the end of the study.

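### Safety is said to rest on the difference between arms in severe adverse events, but the only final safety interval planned is for the Caphosol arm alone

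*Combined protocol and SAP*

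**What the plan says.** Section 2.1 lists tolerability of Caphosol four times daily as a primary objective. Section 10.1 gives the basis for judging it: "Safety and tolerance will be based on the differential incidence of severe adverse events". The same section describes sequential boundaries, one to "terminate the study if the difference in adverse events occurs at a rate of 10% or greater at the interim analysis" at the end of month 3 and another for a 5% differential. Both are stopping devices.

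Section 10.2 does not mention safety. Its method for binary data is general: "Comparisons of binary outcomes such as prevention of oral mucositis will use logistic analysis or Fisher's exact test if the numbers are small".

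Section 10.3 takes a different line from 10.1: "For toxicity, which can only be estimated in the treatment group, 48 subjects in the Caphosol group will allow estimation of a 95% confidence interval" (half-width stated as about 15 points). This is produced first at 20 patients per arm and again at completion: "both an interim analysis and an analysis at the end of the study will be used to estimate the 95% CI". The same paragraph also says that 20 per group can detect a 0.6-unit difference on a toxicity scale, which is a two-group statement.

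No section gives an interval for the between-arm difference in severe adverse events, or says what result at the final analysis would support a favourable conclusion.

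**The concern.** The patients are children and young adults on chemotherapy chosen for its mucosal toxicity. Severe adverse events will occur in both arms for reasons unrelated to the rinse. The only quantity that bears on Caphosol is therefore the excess over control, which 10.1 recognises. The analysis that 10.3 sets out does not estimate it.

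With no interval for the difference, an analyst is left with two options: a Caphosol-arm percentage with nothing to compare it with, or the general test in 10.2, whose non-significance is weak evidence at this sample size. Section 10.3 calls the trial a pilot for a larger study, so whatever is written about safety is likely to be carried forward.

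**Working it through.** **Inputs from the plan.** 48 patients per arm (Synopsis, 10.3); alpha 0.05 (10.3, stated for efficacy, sidedness not given); differences of 10 and 5 points (10.1, for stopping boundaries); logistic analysis or Fisher's exact test for binary outcomes (10.2). **Assumed.** The control severe-event rate, which the documents do not give: 2% to 50%. A two-sided test. No dropout.

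**1. The plan's own figure.** The single-arm half-width is 1.96 × √(p(1−p)/48). At p = 0.5 this is 1.96 × √(0.25/48) = 0.141, or ±14.1 points. The exact (Clopper-Pearson) interval for 24/48 is 35.2% to 64.8%, or ±14.8. The stated ±15% reproduces as the worst case for one arm of 48.

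**2. What that interval leaves out.** Suppose 10 of 48 Caphosol patients (20.8%) have a severe event. The exact interval is 10.5% to 35.0%. It is the same whether control had 10/48, an observed excess of zero, or 5/48, an observed excess of 10.4 points.

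**3. The interval for the difference in that example.** For 10/48 v 5/48, two-sided Fisher p = 0.26. The Wilson limits are 11.7% to 34.3% for Caphosol and 4.5% to 22.2% for control. Newcombe's method gives:

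- upper limit: 0.104 + √((0.343−0.208)² + (0.104−0.045)²) = 0.251
- lower limit: 0.104 − √((0.208−0.117)² + (0.222−0.104)²) = −0.044

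The test is non-significant, yet the data are compatible with an excess of up to 25 points.

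**4. How often the 10.2 test would miss a 10-point excess, if it were used.** Exact enumeration of all 49 × 49 outcomes, summing the probability of those with Fisher p ≤ 0.05 in the harmful direction. The last column is the chance, when the true rates are equal, that the Newcombe 95% upper limit falls below 10 points.

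| Control rate | Power, true +10 points | Missed | Upper limit < 10 points, equal rates |
|---|---|---|---|
| 2% | 28.9% | 71.1% | 62.3% |
| 5% | 22.7% | 77.3% | 44.9% |
| 10% | 18.2% | 81.8% | 33.7% |
| 20% | 14.5% | 85.5% | 23.6% |
| 30% | 12.2% | 87.8% | 19.1% |
| 40% | 12.0% | 88.0% | 17.6% |
| 50% | 12.0% | 88.0% | 17.9% |

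Fisher is conservative. Over the same control rates, a one-sided Fisher test misses 56% to 81% and an uncorrected two-sided z-test about 45% to 83%.

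**5. Whether the interval would mislead.** With a true 10-point excess, the Newcombe upper limit falls below 10 points in only 1.6% to 2.8% of trials over these control rates.

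**The case against.** A reader might infer that the trial will declare Caphosol safe if the arms do not differ significantly. The documents do not say this. No section assigns a significance test to the severe-event difference, and the only example 10.2 gives for its binary method is prevention of mucositis. What 10.3 describes for the end of the study is estimation. It would also be wrong to say the plan has no upper bound for safety: the Caphosol-arm interval has an upper limit. What is missing is a limit on the difference.

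Nor is 71% to 88% the chance that the trial overlooks harm. It applies to one test at the final analysis, rests on assumed control rates, and leaves out the sequential monitoring. That boundary is not specified, so its contribution cannot be calculated. The 10 points are a month-3 stopping trigger and the plan also names 5, so neither can be treated as a final margin that the plan has adopted.

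A further defence is that the two sections mean different things: severe events of any cause in 10.1, and side effects attributed to Caphosol in 10.3. The second can arise in only one arm, and section 5.0 collects such side effects by diary on that arm only. The plan does not draw this distinction, and 10.3 itself speaks of a between-group difference in toxicity. Even on this reading, the comparison named in 10.1 has no interval.

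These points limit the claim. They leave standing the conflict between 10.1 and 10.3 and the absence of an interval for the difference.

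**Conclusion.** The point holds in limited form. Sections 10.1 and 10.3 give incompatible bases for the safety conclusion, and the final analysis that is described cannot show an excess due to Caphosol because both arms receive chemotherapy. This follows from the text and needs no assumption.

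The size is conditional. If the 10.2 test were applied to safety, a true 10-point excess would be missed 71% to 88% of the time with two-sided Fisher at 0.05, 48 per arm and control rates of 2% to 50%, or roughly 45% to 83% with less conservative tests. Under every one of these choices non-significance is poor evidence of safety. The documents support neither the inference that the plan intends that reading nor the use of 10 points as a binding final margin. The change is worth making, but the gap does not invalidate the trial.

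**What to change.** Reconcile 10.1 and 10.3 with text along these lines: the final safety analysis is the Caphosol-minus-control difference in the proportion of patients with at least one severe adverse event, with a 95% confidence interval (for example Newcombe); the upper limit is reported as the largest excess not excluded; a non-significant difference will not be described as evidence of safety; the Caphosol-arm interval is descriptive. The upper limit may be set beside the 10-point and 5-point figures for context, but not as a required margin.

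State which grades count as severe, and capture those events identically in both arms. This may take more than wording. The table in 8.1 marks expected Grade 3 events as not required, 8.2 makes documentation depend on grade, expectedness and relationship, and diary side effects are collected on the Caphosol arm only. If those rules also govern what enters the database, the case report form needs a matching change.

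No more patients are needed. The cost is a less favourable statement: with truly equal rates the upper limit falls below 10 points in about 62% of trials at a 2% event rate, 34% at 10% and 18% to 24% at 20% to 50%. Otherwise the report will say that an excess of that size was not excluded, which is what the data would show.
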